Data will be collected from subjects at two main time points. The baseline interview will occur at or shortly after recruitment, that is, approximately seven days prior to release from the institution. The follow-up assessment will occur 12 months following release to parole. This assessment point will include interviews with all subjects who can be contacted and collection of treatment participation data from programs. In addition to measures of individual-level performance, the study will also collect data to enable an assessment of the system impact and cost implications of the intervention.

BASELINE INTERVIEW

Baseline interviews will be conducted at the prison substance abuse programs in private offices at SATF or in a private room at Walden House. The baseline assessment, administered within two week of recruitment into the study, will include information on demographic characteristics, criminal history, risk level, drug use history, treatment history, participation in prison treatment, psychological status, motivation, perceived coercion, and HIV/AIDS risk. Measures of other variables will be collected from standard instruments. Locator data to assist in later follow-up tracking will also be collected. See Table 4 for the list of instruments or measures and their assessment points.

FOLLOW-UP DATA COLLECTION: 12 MONTHS

For the 12-month assessment, interviewers will meet with participants at locations that are safe, ensure privacy, and minimize travel costs. If participants are incarcerated, they will be interviewed in jail or prison. If a face-to-face follow-up interview is not feasible (e.g., client located out of state), the interview will be conducted by telephone. At the interview, research staff will obtain information on recidivism and criminal activity, drug use, and psychosocial functioning (see Table 3). Records data on treatment participation and criminal justice involvement will also be obtained.

DATA SOURCES - RESEARCH DOCUMENTATION FORMS

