Drug Testing. Since subjects will be recruited in prison, we will not conduct urine tests at baseline since the institution would require that any positive test results be reported to institutional staff, which would violate subject confidentiality. At the 12-month interview, participants will be asked to provide a urine specimen to test for illicit drugs. For clients interviewed in jail or prison at the 12-month assessment, testing for illicit drugs will not be conducted. Urine samples will be collected using an on-site testing kit, which provides immediate results. Specimens will be tested for marijuana, methamphetamine, cocaine, benzodiazepines, and opiates, which are the drugs typically found among offenders in southern California.

3. *Criminality / Criminal Justice System Involvement*

Lifestyle Criminality Screening Form (LCSF). A risk of recidivism score will be constructed from the Lifestyle Criminality Screening Form (LCSF: Walters, 1990; 1991; 1998). The LCSF consists of 14 items that factor into four scales related to criminal lifestyle: Irresponsibility (non-support of child, school dropout, longest job held, fired/quit job), Self-Indulgence (drug abuse history, marital background, tattoos), Interpersonal Intrusiveness (any prior intrusive offense, including burglary, robbery, violence against others, arson, and sex offenses, number of intrusive offenses, ever used weapons in an offense, physical abuse of significant others), and Social Rule Breaking (arrest history, age at first arrest, school disciplinary problems). The LCSF scale has good internal consistency (Cronbach alpha = .70) and test-retest reliability ($r = .93$). Walters and McDonough (1998) found that the full-scale score to be more predictive of revocations for federal probationers than scores on the individual scales; thus, the full-scale score will be used in analysis.

Criminal Justice Records. Criminal justice information will be obtained from official records maintained by California criminal justice agencies. Arrest charges and case dispositions are available from the California Department of Justice (the Automated Criminal History System - ACHS). Parole status, parole violations, and reincarcerations are available from the California Department of Corrections and Rehabilitation (the Offender Based Information System - OBIS). ISAP has obtained individual record data from these agencies in electronic format for many previous studies.

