Criminal History. Criminal justice records include only crimes that come to the attention of law enforcement. In order to capture a more complete record of a subject's criminal behavior, the CJ-DATS baseline form includes questions on the type, frequency, and amount of criminal activity for the past six-months and the past thirty-day and on lifetime and recent arrests and incarcerations. The follow-up form asks about criminal activity and CJS involvement during the previous six months or during the six months prior to incarceration, if the subject is interviewed in jail or prison.

Table 4. Instruments and Assessment Schedule

Instruments /Measures	Variables of Interest	Administration Time (approx.)	Data Source	Assessment Points
1. Demographics, Psychosocial				
CJ-DATS form	Demographics, employment, education, family and peer relationships, HIV risk	45 min	Clients	Baseline, FU
2. Drug and Alcohol Use				
Drug Use History	Substance use	In CJ-DATS form	Clients	Baseline, FU
TCU Drug Screen	Substance use severity	10 min	Clients	Baseline
Drug testing	Substance use	5 min	Biochemical	FU
3. Criminality / CJS Involvement				
Lifestyle Criminality Screening Form	Risk for recidivism	10 min	Clients	Baseline
Criminal Justice Records	CJ involvement	N/A	CJ agencies	FU
Criminal History	Criminal activity	In CJ-DATS form	Clients	Baseline, FU
4. Psychological Status				
SCID IV	Anti-social personality disorder	15 min	Clients	Baseline
Brief Symptom Inventory	Psychological symptoms	15 min	Clients	Baseline, FU
Barratt Impulsiveness Scale	Impulsiveness	10 min	Clients	Baseline
5. Treatment				
Client Evaluation of Self at Intake	Motivation and readiness for treatment	10 min	Clients	Baseline
Counseling Utilization Form	Session attendance	N/A	Program records	During intervention
CM Record Form	Adherence to CM protocol	N/A	Client, Staff	During intervention
Treatment Termination Form	Treatment completion status	N/A	Program records	During intervention
Client Satisfaction Questionnaire	Client satisfaction with treatment	10 min	Clients	FU
Dimensions of Sustainability Questionnaire	Assessment of sustainability	10 min	Staff	After intervention
6. Qualitative Assessment				
Information Meeting, Intervention Development Workgroup, Monthly Project Meetings, Focus Groups	Feedback on intervention, acceptability, sustainability	N/A	Staff, Clients	Prior to, during, and after intervention

4. Psychological Status

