Aim 2 For parolees who enter community treatment, determine whether providing incentives for attendance results in greater retention in treatment.

H3. Participants in the Attendance Incentive group will have a longer length of time in treatment than will participants in the Attendance Information group.

Aim 3 For parolees who enter community treatment, determine whether providing an incentive increases the likelihood that clients will participate in HIV testing and counseling.

H4. Participants in the Attendance Incentive group will be more likely to agree to receive HIV testing and to participate in post-test counseling than will participants in the Attendance Comparison group.

Aim 4 Assess the long-term impact of the use of incentives on drug use, crime, and psychosocial outcomes at 12 months following the end of the six-month intervention.

H5. Participants in the Attendance Incentive group will be more likely to be abstinent than will participants in the Attendance Information group at the Month 12 assessment.

H6. Participants in the Attendance Incentive group will have a lower percentage of arrests and reincarcerations than will participants in the Attendance Information group at the Month 12 assessment.

H7. Participants in the Attendance Incentive group will have better psychosocial outcomes (employment, education, family relationships, psychological functioning, and HIV risk) than will participants in the Attendance Information group at the Month 12 assessment.

Aim 5 Assess the long-term impact of the use of incentives to promote treatment participation on HIV-risk behaviors at 12 months following the end of the six-month intervention.

H8. At the Month 12 assessment, participants in the Attendance Incentive group will report lower levels of injection drug use and engagement in HIV-risk sexual behaviors than will participants in the Attendance Comparison group.

H9. At the Month 12 assessment, participants in the Attendance Incentive group will report greater participation in HIV-related services (of any type) over the period since discharge from Walden House than will participants in the Attendance Comparison group.

Aim 6 Assess issues of acceptability, satisfaction, and sustainability of the use of incentives to increase enrollment and retention among staff and clients.

RQ1. Were clients and treatment staff who participated in the CM intervention accepting of and satisfied with the use of incentives to promote enrollment and attendance?

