Treatment retention. Retention will be measured as both a categorical and a continuous variable. Treatment completion will be coded as yes or no and will be defined as attending the Walden House program for 26 weeks or leaving under favorable circumstances (e.g., clinically approved early discharge, transfer to another program, moving to another county). Treatment retention will be measured as the number of days of attendance at Walden House (up to a maximum of 26 weeks or 180 days).

Substance use. For the follow-up period, recent substance use will be defined as either self-report of use or a positive drug test result. Recency and frequency measures of substance use from the CJ-DATS form will also be used.

Criminal justice involvement and criminal activity. State criminal justice records will be used to determine the number and type of rearrest or reincarceration and the number and type of case dispositions (probation, jail, prison, technical violation, or new conviction) over the 18-month period following release to parole (covering the six-month intervention period and the 12-month follow-up period). These measures will also be considered as binary variables (i.e., any arrest during the specified period vs. none, reincarceration vs. none). Since criminal justice history variables are event based with specific dates, we will also be able to calculate time to rearrest or reincarceration. On the basis of self-report responses on the CJ-DATS form, crime outcomes will also include the total number of crimes committed and the number of crimes committed within specified crime categories (i.e., crimes against persons, property crimes, drug crimes, and other crimes).

Psychosocial functioning. Data on employment, education, and family relationships over the follow-up period are collected by self-report from the CJ-DATS form. Employment variables include employment status, type of job (if employed), hours worked per month, and average monthly income over the previous six-month period. Education variables include type of education (e.g., years of education, GED, vocational training) and any diplomas or certificates obtained. Family relationship variables include living arrangements and number of days that participant had problems getting along with family and others. Psychological functioning will be measured by the composite score from the BSI. HIV-related behaviors (risky sex and drug use) will include items from the CJ-DATS form.

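### The H5 abstinence outcome has two detection rules, self-report plus urine in the community and self-report alone in custody, and H6 expects custody to differ by arm

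*Protocol*

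**What the plan says.** Under Primary Aims, H5 expects that Incentive participants "will be more likely to be abstinent than will participants in the Attendance Information group at the Month 12 assessment". Under Hypothesis Testing (Substance use), the outcome is a composite: "recent substance use will be defined as either self-report of use or a positive drug test result". The same paragraph adds that self-reported recency and frequency of use from the CJ-DATS form will be used as well.

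Under Data Sources, Drug Use (Drug Testing), the general rule is: "At the 12-month interview, participants will be asked to provide a urine specimen to test for illicit drugs". The exception follows: "For clients interviewed in jail or prison at the 12-month assessment, testing for illicit drugs will not be conducted".

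Under Follow-up Data Collection: 12 Months, custody does not remove anyone from the sample: "If participants are incarcerated, they will be interviewed in jail or prison". Where a face-to-face interview is not feasible, a telephone interview is allowed. Participant Reimbursement makes the specimen voluntary.

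Under Criminal History, the follow-up form asks about crime and justice involvement over the previous six months, or "during the six months prior to incarceration, if the subject is interviewed in jail or prison". No matching window is stated for drug use, and the word recent in the composite is not defined.

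H6 reads: "Participants in the Attendance Incentive group will have a lower percentage of arrests and reincarcerations than will participants in the Attendance Information group".

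**The concern.** One binary outcome is measured in two ways. In the community, a man who uses and denies it can still be identified by urine. In jail or prison he cannot, and the either/or definition then records him as abstinent rather than as missing. Telephone interviews and refused specimens have the same effect, though the Protocol gives no reason to expect those to differ by arm. For custody it does give one, namely H6.

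If the intervention works as hypothesised, the Information arm has more men in custody at interview and so more undetected use. The H5 contrast is then pushed against Incentive.

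The safeguards elsewhere do not reach this problem. The likelihood-based and imputation methods and the attrition checks under Design Analyses deal with absent data and dropout, whereas these men have a recorded value. The same section relies on announcing a urine request to encourage candid answers, but in custody no test follows.

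A second difference arises if the drug-use questions cover time spent in custody. Restricted access to drugs would then count as abstinence.

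**Working it through.** **The plan's own figures.** The Protocol gives no figure for this bias. The only stated figure that bears on H5 is power of about .75 for 12-month interview outcomes, at d = 0.30 with about 170 participants (Power Analysis). With 85 per arm, two-sided .05 and a normal approximation, 0.30 × √(85/2) = 1.956 and 1.956 − 1.960 = −0.004, so power is about 0.50. The stated .75 is not reproduced. That is a separate matter, and this point does not rest on it.

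**Inputs**
- From the Protocol: the composite definition, no urine in custody, custody interviews retained, the direction of H6, and about 85 interviewed per arm.
- For scale only: the CDCR evaluations under Preliminary Studies report 12-month return to custody of 24% with aftercare and 15% with 90 or more days of it.
- Assumed, because the Protocol gives no value: true use u = 0.55 in both arms; self-report sensitivity s = 0.6 to 0.8; urine detection of unreported use t = 0.4 to 0.6; custody gap between arms g = 10 to 20 points.

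**Formula.** A user is detected with probability s + (1 − s)t in the community and s in custody. The loss in custody is therefore (1 − s)t. With a custody share c, observed use in an arm is

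u × [s + (1 − c)(1 − s)t].

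This assumes a pre-incarceration window, so that true use does not depend on setting, and a specimen from everyone in the community. If u is equal in both arms, the false difference in abstinence (Incentive minus Information) is

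−u × g × (1 − s)t.

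**Results with no true difference**

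| Custody gap g | s | t | u × g × (1 − s)t | False difference |
|---|---|---|---|---|
| 0.10 | 0.8 | 0.4 | 0.55 × 0.10 × 0.08 | −0.4 points |
| 0.20 | 0.6 | 0.6 | 0.55 × 0.20 × 0.24 | −2.6 points |
| 0.09 (24% − 15%) | 0.8 | 0.4 | 0.55 × 0.09 × 0.08 | −0.4 points |
| 0.09 (24% − 15%) | 0.6 | 0.6 | 0.55 × 0.09 × 0.24 | −1.2 points |
| 0 | any | any | 0 | 0 |

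**Scale.** At 85 per arm and proportions near 0.5, the standard error of a difference is √(2 × 0.25/85) = 0.077, or 7.7 points. The bias is therefore between 0.4/7.7 = 0.05 and 2.6/7.7 = 0.34 standard errors. If abstinence were 50% in the Information arm, the assumed 12-month effect of 0.30 on the arcsine scale would put Incentive at 64.8%, a difference of 14.8 points.

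**The case against.** The strongest case on the other side has five parts.

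- **The recall window may exist.** The Protocol says the CJ-DATS form captures the timing and frequency of use. The instruments are not in the text at hand, and the same follow-up form already uses a pre-incarceration window for crime. This stands: one can say only that no drug-use window is stated. Even with one, the urine half of the definition still applies only outside custody.
- **Self-report measures are already planned.** This also stands in part. Recency and frequency items exist in every setting and come close to a setting-neutral outcome, but they are not tied to H5 or to a common window.
- **Custody at interview is not H6.** H6 concerns reincarceration over the period. The 15% and 24% appear to be cumulative 12-month rates, compared by attendance rather than by randomised arm. The two are linked but not identical, so the custody gap remains an assumption.
- **Detail may be left to a statistical analysis plan.** That is fair for tabulations and sensitivity analyses. It is less so for the composite, which the Protocol itself fixes, or for a recall window, which must be in the form before the interviews are held.
- **Not testing in custody may have good reasons.** The Protocol cites confidentiality for not testing at baseline in prison, and nothing here requires testing in custody.

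A reader might go further and infer that the missing urine could erase or reverse a real effect. The documents do not support that. Suppose community use is 45% vs 60%, use in custody is 10%, custody shares are 25% vs 40%, s = 0.7 and t = 0.5. True use over everyone is then 0.75 × 0.45 + 0.25 × 0.10 = 36.25% vs 0.60 × 0.60 + 0.40 × 0.10 = 40.0%, a gap of 3.75 points. Observed use is 30.4% vs 33.4%, a gap of 2.96. With urine in custody at the same detection rate, the gap would be 3.75 × 0.85 = 3.19. Missing urine accounts for about 0.2 points, and the direction is unchanged. The rest of the distance from the 15-point community gap comes from assuming little use in custody. H5 asks who is abstinent at the Month 12 assessment, and a man not using in custody is abstinent on that wording. That part is a question of recall window and estimand, not of test sensitivity.

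**Conclusion.** The point holds as a defect in the definition of a secondary outcome. The composite detects use less well in custody, the Protocol keeps those interviewed in custody in the sample, and its own H6 gives a reason to expect custody to differ by arm. If it does, the bias runs against Incentive.

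The size cannot be derived from the documents. Missing urine alone gives about 0.4 to 2.6 points under the stated assumptions, about 0.4 to 1.2 at a 15% vs 24% custody split, and no false difference if custody shares are equal. This is small beside sampling error at 85 per arm, but it is systematic and cheap to address. Any further difference comes from restricted access to drugs in custody, and depends on the recall window and on which estimand H5 is meant to address.

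**What to change.** - Under Criminal History and Hypothesis Testing (Substance use), apply the existing pre-incarceration window to the drug-use items for those interviewed in custody, and define what counts as recent.
- Alongside the composite, prespecify an H5 analysis that uses self-report over that window in every interview setting. Report the composite restricted to participants eligible for urine testing as supportive.
- Tabulate interview setting (community, custody, telephone) and urine availability by arm.
- Optionally, add a sensitivity analysis that treats reincarceration as non-abstinence. It mixes H6 into H5, so it should not be more than that.

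The cost is the wording of one outcome definition, a check of the follow-up form, and one added analysis. There are two downsides: the setting-neutral analysis rests on self-report, and its window covers different calendar time for those in custody. Keeping the composite in the plan limits the first.
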